8.4.3 Safety - amended

The incidence of treatment-emergent AEs (TEAEs) will be tabulated by treatment group. Adverse events are considered to be treatment-emergent if they have started or worsened after first application of study drug up to 2 days after end of treatment with study drug. Further tables will be produced for serious and/or drug-related treatment-emergent AEs, also treatment-emergent AEs leading to discontinuation of study drug and of special safety interest. The incidence of AEs during pre-treatment and during follow-up (ie, AEs occurring more than 2 days after end of treatment with study drug) will be tabulated separately. In addition to the summary tables of AEs, listings of SAEs, AEs leading to discontinuation of study drug and AEs of special safety interest will be provided.

Mortality in the study will be summarized descriptively. Any deaths in the study period will be listed, with day of death relative to start and stop of study drug and cause of death. Mortality is also defined as an exploratory efficacy parameter, and so being a binary outcome the difference in occurrence between treatment groups will be analyzed as described in Section 8.4.2.

The safety evaluation of laboratory data will include:

- Incidence rates of treatment-emergent laboratory values outside of normal range
- Incidence rates of pre-specified laboratory data abnormalities
- Descriptive analysis of continuous laboratory parameters and their changes from baseline by treatment group and visit.

Descriptive analysis of vital signs and their changes from baseline will be performed by treatment group and visit. Descriptive statistics of pulse oximetry and blood pressure/heart

rate measurements for the assessment of orthostatic changes will be performed by treatment group and visit.¹³³

For ECGs, the status pre-treatment and post treatment-initiation will be tabulated. The incidence rates of treatment-emergent ECG abnormalities will be tabulated by treatment group. A descriptive analysis of continuous ECG parameters and their changes from baseline by treatment group and visit will also be presented.

8.4.4 Pharmacokinetics

For the investigation of PK, the plasma concentrations of riociguat and its main metabolite M-1 (BAY 60-4552) will be determined at the times given in Section 7.4 using a sparse sampling approach.

The data processing and the statistical analysis will be performed in accordance with the sponsor's current guidelines.

Riociguat and its main metabolite M-1 (BAY 60-4552) peak and trough concentrations will be summarized by visit, separated according to actual dose.

8.5 Planned interim analyses - amended

A formal interim analysis of the main treatment phase is not planned. The main treatment phase will be unblinded for data analysis when the last patient completes the main treatment phase (Visit 12)¹³⁴ and the database for the main treatment phase is declared clean, whichever occurs last.

The first safety update will be performed on the long-term extension phase when the last patient completes 24 weeks of treatment (Visit 19)¹³⁵. Safety updates then will be performed at least yearly until the last patient completes the entire study, when a final analysis will be conducted.

8.6 Determination of sample size - amended

There is lack of positive trials in dcSSc. Most trials have used change in mRSS to Month 6 or Month 12 as the primary endpoint, and 4 published articles are referenced for the estimate of variability in this study (Table 8-1).

¹³³ Per Amendment 6

¹³⁴ Per Amendment 5

¹³⁵ Per Amendment 5

Table 8–1 References for estimate of variability

Reference	Trial treatment	Active arm SD	Placebo arm SD
Postlethwaite (2008)[35]	Collagen 0 – 12 months	7.6	7.7
Khanna (2009)[26]	Relaxin 0 – 24 weeks	7.0	7.0
Merkel (2012)[36]	0 – 6 month meta-analysis		7.2
	0 – 12 month meta-analysis		8.4
Amjadi (2009)[37]	D-Pen		8.6
	Relaxin		7.0
	Collagen		7.1

Abbreviations: D-Pen = D-penicillamine; SD = standard deviation.

Taking these sources into account, a reasonable upper bound for the estimate of the standard deviation to be used in the sample size calculation of this study has been taken as 8.0.

One of the components of exploratory efficacy measure¹³⁶ mRSS progression is a 5 point or more deterioration from baseline to any assessment in the 12 month study period, this being considered a clinically meaningful change [14]. For the primary sample size calculation based on change in mRSS from baseline to Week 52, a slightly more conservative 4-point difference between riociguat and placebo has been taken, given that the trials referenced above never achieved a 5-point, or even a 4-point, superiority of active over placebo.

The primary efficacy estimand in this study will be change in mRSS from baseline to Week 52. Assuming a standard deviation of 8 points, a power of between 70% and 80% and a two-sided significance level of 5%, with a 1:1 randomization, then to detect a placebo-adjusted difference of 4 points, between 51 and 64 patients in each treatment group, a total of 102 to 128 patients, would be required to be valid for the ITT analysis (see Table 8–2). Allowing for up to two patients randomized and not treated, approximately 130 randomized patients are planned.¹³⁷

Table 8–2 Power calculations: power varying from 70% to 80% in 2% stages¹³⁸

N per group	51	53	56	58	61	64
Total N	102	106	112	116	122	128
Power (%)	70	72	74	76	78	80

N = number of patients

Sources of these sample size and power calculations are nQuery version 7.0, module MTT0-1.¹³⁹

¹³⁶ Per Amendment 4

¹³⁷ Per Amendment 5

¹³⁸ Per Amendment 5

¹³⁹ Per Amendment 5

9. Data handling and quality assurance

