4.1 Design overview -amended

[figure not shown]
In this multinational, multicenter, randomized (1:1), double-blind, placebo-controlled, parallel-group study, a total of approximately 200 patients are planned for enrollment in order to randomize up to⁹ approximately 130 patients to study drug treatment (approximately 65 patients to the riociguat group and 65 to the placebo group).

The study design consists of a main treatment phase followed by a long-term extension phase as follows (see [Figure 4–1](#) and [Figure 4–2](#)):

- **Screening phase:** up to 2 weeks
- **Main treatment phase:** 52 weeks of double-blind treatment, consisting of:
 - Dose titration period of up to 10 weeks
 - Maintenance period of up to 42 weeks
- **Long-term extension phase**
 - Dose-titration period of up to 10 weeks (double-blind)
 - Open-label extension period
- **Termination visit and safety follow-up visit**

[figure not shown]
⁹ Per Amendment 5

Figure 4–1 Main treatment phase design

Abbreviations: V = visit; R = randomization; TID = 3 times a day.

Figure 4–2 Long-term extension phase design

Abbreviations: TID = 3 times a day; V = visit.

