5.1 Eligibility

5.1.1 Inclusion criteria - amended

Patients must meet the following criteria to be eligible for enrollment in the study:

1. Written informed consent
2. Men or women aged 18 years and older
3. Systemic sclerosis, as defined by ACR/EULAR 2013 criteria[1]
4. dcSSc according to the LeRoy criteria[3] ie, skin fibrosis proximal to the elbows and knees in addition to acral fibrosis²².
5. Disease duration of ≤ 18 months (defined as time from the first non-Raynaud's phenomenon manifestation)
6. ≥ 10 and ≤ 22 mRSS units at the screening visit
7. FVC $\geq 45\%$ of predicted at screening
8. DL_{CO} $\geq 40\%$ of predicted (hemoglobin-corrected) at screening
9. Negative serum pregnancy test in a woman of childbearing potential at the screening visit
10. Women of childbearing potential must agree to use adequate contraception when sexually active. "Adequate contraception" is defined as any combination of at least 2 effective methods of birth control, of which at least 1 is a physical barrier (eg, condom with hormonal contraception like implants or combined oral contraceptives, condom with intrauterine devices). This applies since signing of the informed consent form until 30 (+5) days after the last study drug administration.
11. Ability to comply with the clinical visits schedule and the study-related procedures

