8.4.2.1 Primary endpoint¹²¹

The primary analysis will be the change in mRSS from baseline to all assessments post baseline up to Week 52 using mixed model repeated measures (MMRM) with baseline mRSS as a covariate, fixed effects treatment arm and region, the interaction effect between study visit and treatment arm, and patient specific random effects to account for both heterogeneity among patients and correlation among measurements taken on the same patient with an unstructured covariance assumption. The main estimand of interest is the treatment difference

¹²⁰ Per Amendment 1

¹²¹ Per Amendment 4

between the riociguat and placebo treatment arms at Week 52. The null hypothesis to be tested is no difference between riociguat and placebo at this visit.

The model statement is:

$$Y_{ij} = \mu + \beta X_i + t_k + r_l + v_j + (tv)_{jk} + s_i + \varepsilon_{ij}$$

where Y_{ij} is the change from baseline in mRSS to visit j for subject i that is in treatment group k and region l ; μ is the intercept, β is the baseline covariate effect, X_i is the baseline mRSS for subject i , t_k is the fixed effect of treatment k , r_l is the fixed effect of region l , v_j is the fixed effect of visit j , $(tv)_{jk}$ is the interaction effect of treatment k by visit j , s_i is the random effect of subject i and $\varepsilon_{ij} \sim \text{Normal}(0, \sigma^2)$ represents the residual variance component with $\text{corr}(\varepsilon_{ij}, \varepsilon_{ij'}) = \rho_{jj'}$, $j \neq j'$

As a sensitivity analysis, the MMRM using the above model will also be applied to assessments post-baseline up to termination of study medication or initiation of rescue medication. In addition, the MMRM on all assessments will be repeated including additional effects time on rescue medication and time on study medication. MMRM assumes missing at random; mRSS by time of patient discontinuation from study medication¹²² will be summarized and further methods using multiple imputation that allow for missing data not at random will be investigated. Details of such methods will be described in the SAP.

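### Does calling an SD of 8.0 an upper bound overstate the planned power, when Table 8-1 lists 8.4 and 8.6?

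*Protocol*

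**What the plan says.** Protocol Section 8.6 draws on four published sources, set out in Table 8-1, and then adopts 8.0 as "a reasonable upper bound for the estimate of the standard deviation to be used in the sample size calculation". One row of that table is headed "0 – 12 month meta-analysis" and gives a placebo SD of 8.4. The D-penicillamine row gives 8.6 with no time point.

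The power statement is tied to the chosen SD: "Assuming a standard deviation of 8 points, a power of between 70% and 80" per cent, "to detect a placebo-adjusted difference of 4 points, between 51 and 64 patients in each treatment group, a total of 102 to 128 patients". Table 8-2 steps through the numbers per arm from 51 to 64 and does not vary the SD. Section 4.1 plans "approximately 65 patients to the riociguat group and 65 to the placebo group".

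Two other provisions bear on the SD that will apply. Section 5.1.1 restricts entry to "≥ 10 and ≤ 22 mRSS units at the screening visit". Section 8.4.2.1 analyses the primary endpoint "using mixed model repeated measures (MMRM) with baseline mRSS as a covariate".

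**The concern.** Read quickly, an upper bound is a value the evidence does not exceed, and two of the nine listed SDs do exceed it. One of them, 8.4, is labelled 0 to 12 months, the same horizon as the Week 52 endpoint. No reason is given for setting either aside.

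If variability is larger than planned, power is smaller than planned. A reader told that 8.0 is an upper bound would take 70% to 80% as a floor. If the true SD were 8.4 or 8.6 in both arms, 80% power would need 71 or 74 patients per arm (142 or 148 in total) instead of 64 (128 in total).

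**Working it through.** **Inputs (Protocol Section 8.6).** Difference 4 points, two-sided 5%, 1:1 allocation, common SD 8.0, n per arm 51 to 64. Table 8-1 gives these SDs:

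| Source | Active | Placebo column |
|---|---|---|
| Collagen trial, 0–12 months | 7.6 | 7.7 |
| Relaxin trial, 0–24 weeks | 7.0 | 7.0 |
| Meta-analysis, 0–6 months | – | 7.2 |
| Meta-analysis, 0–12 months | – | 8.4 |
| Three-trial analysis: D-penicillamine / relaxin / collagen, no time given | – | 8.6 / 7.0 / 7.1 |

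**Step 1: reproduce Table 8-2.** For a two-sample t-test the noncentrality parameter is 4 / (SD × √(2/n)), with 2n − 2 degrees of freedom.
- n = 51, SD 8: 4 / (8 × √(2/51)) = 2.525; critical t 1.984; power 70.6%.
- n = 64, SD 8: 4 / (8 × √(2/64)) = 2.828; critical t 1.979; power 80.1%.
- n = 53, 56, 58 and 61 give 72.2%, 74.6%, 76.1% and 78.2%.

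Every column of Table 8-2 reproduces.

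**Step 2: place 8.0 among the sources.** The nine SDs sum to 67.6, so their mean is 67.6 / 9 = 7.51; the median is 7.2. Seven of the nine are below 8.0. The three labelled 12 months average (7.6 + 7.7 + 8.4) / 3 = 7.9. So 8.0 is on the high side of the full list and close to the centre of the 12-month values. It is not the maximum.

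**Step 3: vary the SD in both directions.** Where the arms differ, the pooled SD is √((active² + placebo²) / 2).

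| SD assumption | Power, 51 per arm | Power, 64 per arm |
|---|---|---|
| 7.0 both arms | 81.5% | 89.4% |
| 7.5 both arms (about the source mean) | 76.0% | 84.9% |
| 8.0 both arms (plan) | 70.6% | 80.1% |
| Placebo 8.4, active 7.6 (pooled 8.01) | 70.5% | 80.1% |
| Placebo 8.6, active 7.6 (pooled 8.12) | 69.3% | 79.0% |
| Placebo 8.4, active 8.0 (pooled 8.20) | 68.4% | 78.2% |
| 8.4 both arms | 66.3% | 76.2% |
| 8.6 both arms | 64.3% | 74.2% |

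At the planned 65 per arm, power is 80.8% at SD 8.0, 76.9% at 8.4 and 74.9% at 8.6. The active SDs of 7.6 and 8.0 paired with the higher placebo values are assumptions; 7.6 is the only 12-month active SD in Table 8-1.

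**Step 4: when does 8.0 still hold?** With placebo at 8.4, the pooled SD stays at or below 8.0 if the active SD is at most √(128 − 8.4²) = 7.58. With placebo at 8.6, the limit is √(128 − 8.6²) = 7.35.

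**Step 5: how much would covariate adjustment have to recover?** The calculation is an unadjusted t-test, whereas the primary model adjusts for baseline mRSS. To bring 8.4 down to an effective 8.0, the model must explain 1 − (8/8.4)² = 9.3% of the variance; from 8.6, 1 − (8/8.6)² = 13.5%. These correspond to correlations of about 0.31 and 0.37. The documents give no such correlation, so this shows only the size of the gap, not that it closes.

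**The case for a change.** The best case for changing the text is that the label and the table disagree on the same page. The 8.4 is one of only three SDs at the right horizon, while several of the lower values come from 24-week or 6-month follow-up. The count of seven in nine may also flatter 8.0, because relaxin and collagen each appear in two sources. The calculation has little other stated margin: it allows for two patients randomized but not treated and makes no allowance for missing Week 52 data. Because Table 8-2 never varies the SD, the reader cannot see how sensitive power is to it.

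What stands is that 8.0 is neither a worst case nor the largest listed value, and *planning value* would describe it more exactly. What does not stand is that the stated power is wrong or that 8.0 is an optimistic choice. The phrase concerns a single estimate drawn from several sources, which need not equal their maximum, and the two larger figures are shown openly beside it. A sensitivity display confined to SDs above 8.0 would be one-sided, since power is higher than stated at most of the listed values.

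**Conclusion.** The wording is imprecise, but the plan needs no change. The stated power is correctly calculated for the SD it names, and that SD is a reasonable choice from the sources given.

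The possible shortfall runs from nothing to about 6 percentage points. The upper end requires 8.4 or 8.6 to hold in both arms, although both are placebo-column figures with no active SD beside them. If only the placebo arm is that variable and the active SD is 7.6, the loss is about 0 to 1 point; with placebo 8.4 and active 8.0 it is about 2. All these figures assume complete Week 52 data and give no credit for baseline adjustment or earlier visits. The documents do not say whether the trials behind 8.4 and 8.6 resembled a population restricted to mRSS 10 to 22, so no loss is established for this trial.

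Nor would a correction gain anything. Section 13.4.1 records that recruitment was complete by Amendment 6, and the rationale for Amendment 7 refers to main-phase results already in hand. The SAP covers only the descriptive analysis of the extension. What the trial can say about the treatment effect now rests on the two-sided 95% confidence intervals specified in Section 8.4.2.1, not on prospective power. A reader who wants to judge the planning SD has all nine source values in Table 8-1.

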9.1 Data recording

It is the expectation of the sponsor that all data entered into the eCRF has source documentation available at the site. The site must implement processes to ensure this happens. A source document checklist will be used at the site to identify the source data for all data points collected and the monitor will work with the site to complete this.

Specific data may be entered directly into the eCRF according to instructions provided in the eCRF completion manual.

Data recorded from “only screened patients (screening failures)”

Data of 'only screened patients' will be recorded at least as source data, as far as the reason for the premature discontinuation is identifiable. At minimum, data to be recorded in the eCRF are demographic information (patient number, date of birth/age, sex and ethnicity), inclusion and exclusion criteria, the reason for premature discontinuation and date of last visit. These data will be transferred to the respective database.

For screening failures with an SAE, the following additional data should be collected in the eCRF, in addition to demographic information, primary reason for discontinuation and date of last visit:

- All information about the SAE
- All information related to the SAE such as:
 - Concomitant medication
 - Medical history
 - Other information needed for SAE complementary page

9.2 Monitoring

In accordance with applicable regulations, GCP, and sponsor's/clinical research organization's (CRO's) procedures, monitors will contact the site prior to the start of the study to review with the site staff the protocol, study requirements, and their responsibilities to satisfy regulatory, ethical, and sponsor's requirements. When reviewing data collection procedures, the discussion will also include identification and documentation of source data items.

The sponsor/designee will monitor the site activity to verify that the:

- Data are authentic, accurate and complete
- Safety and rights of patients are being protected
- Study is conducted in accordance with the currently approved protocol (including study treatment being used in accordance with the protocol)
- Any other study agreements, GCP, and all applicable regulatory requirements are met.

The investigator and the head of the medical institution (where applicable) agrees to allow the monitor direct access to all relevant documents.

9.3 Data processing

The data collection tool for this study will be a validated electronic system called Medidata Rave. Patient data necessary for analysis and reporting will be entered/ transmitted into a validated database or data system (eg, TOSCA V4 3_1_1; SAS 9.2). Clinical data management will be performed in accordance with applicable sponsor's standards and data cleaning procedures. This is applicable for data recorded on eCRF as well as for data from other sources (eg, IxRS, laboratory, ECG).

For data coding (eg, AEs, medication), internationally recognized and accepted dictionaries will be used. After its initial release for biometrical analysis, the clinical database is planned to be re-opened for the inclusion of the following additional data: eg, PK data, biomarker¹⁴⁰ data.

9.4 Audit and inspection

To ensure compliance with GCP and regulatory requirements, a member of the sponsor's (or a designated CRO's) quality assurance unit may arrange to conduct an audit to assess the performance of the study at the study site and of the study documents originating there. The investigator/institution will be informed of the audit outcome.

In addition, inspections by regulatory health authority representatives and IEC(s)/IRB(s) are possible. The investigator should notify the sponsor immediately of any such inspection.

The investigator/institution agrees to allow the auditor or inspector direct access to all relevant documents and allocate his/her time and the time of his/her staff to the auditor/inspector to discuss findings and any issues. Audits and inspections may occur at any time during or after completion of the study.

9.5 Archiving

Essential documents shall be archived safely and securely in such a way that ensures that they are readily available upon authorities' request.

Patient (hospital) files will be archived according to local regulations and in accordance with the maximum period of time permitted by the hospital, institution or private practice. Where the archiving procedures do not meet the minimum timelines required by the sponsor, alternative arrangements must be made to ensure the availability of the source documents for the required period.

The investigator/institution notifies the sponsor if the archival arrangements change (eg, relocation or transfer of ownership).

The investigator site file is not to be destroyed without the sponsor's approval.

The contract with the investigator/institution will contain all regulations relevant for the study center.

¹⁴⁰ Per Amendment 5

10. Premature termination of the study

The sponsor has the right to close this study (or, if applicable, individual segments thereof [eg, treatment arms; dose steps; centers]) at any time, which may be due but not limited to the following reasons:

- If risk-benefit ratio becomes unacceptable owing to, for example,
 - Safety findings from this study (eg, SAEs)
 - Results of any interim analysis
 - Evaluation of risk-benefit at any time in the study where a lack of substantial treatment benefit is shown
 - Results of parallel clinical studies
 - Results of parallel animal studies (on eg, toxicity, teratogenicity, carcinogenicity or reproduction toxicity).
- If the study conduct (eg, recruitment rate; drop-out rate; data quality; protocol compliance) does not suggest a proper completion of the trial within a reasonable time frame.

The investigator has the right to close his/her center at any time.

For any of the above closures, the following applies:

- Closures should occur only after consultation between involved parties. Final decision on the closure must be in writing.
- All affected institutions (eg, IEC(s)/IRB(s); competent authority(ies); study center; head of study center) must be informed as applicable according to local law.
- All study materials (except documentation that has to remain stored at site) must be returned to the sponsor. The investigator will retain all other documents until notification given by the sponsor for destruction.
- In case of a partial study closure, ongoing patients, including those in post study follow-up, must be taken care of in an ethical manner.

Details for individual patient's discontinuation¹⁴¹ can be found in Section 5.2.1.

11. Ethical and legal aspects

11.1 Ethical and legal conduct of the study

The procedures set out in this protocol, pertaining to the conduct, evaluation, and documentation of this study, are designed to ensure that the sponsor and investigator abide by GCP guidelines and under the guiding principles detailed in the Declaration of Helsinki. The study will also be carried out in keeping with applicable local law(s) and regulation(s).

Documented approval from appropriate IEC(s)/IRBs will be obtained for all participating centers/countries before start of the study, according to GCP, local laws, regulations and organizations. When necessary, an extension, amendment or renewal of the Ethics

¹⁴¹ Per Amendment 4

Committee (EC)/IRB approval must be obtained and also forwarded to the sponsor. The responsible unit (eg, EC/IRB, head of the study center/medical institution) must supply to the sponsor, upon request, a list of the EC/IRB members involved in the vote and a statement to confirm that the EC/IRB is organized and operates according to GCP and applicable laws and regulations.

Strict adherence to all specifications laid down in this protocol is required for all aspects of study conduct; the investigator may not modify or alter the procedures described in this protocol.

Modifications to the study protocol will not be implemented by either the sponsor or the investigator without agreement by both parties. However, the investigator or the sponsor may implement a deviation from, or a change of, the protocol to eliminate an immediate hazard(s) to the trial subjects without prior IEC/IRB/sponsor approval/favorable opinion. As soon as possible, the implemented deviation or change, the reasons for it and if appropriate the proposed protocol amendment should be submitted to the IEC/IRB/head of medical institution/sponsor. Any deviations from the protocol must be explained and documented by the investigator.

Details on discontinuation of the entire study or parts thereof can be found in Section 10.

